#### Documented Hypoglycemia:

- **Documented symptomatic hypoglycemia:** An event during which typical symptoms of hypoglycemia are accompanied by plasma glucose (PG)  $\leq 70$  mg/dL ( $\leq 3.9$  mmol/L).
- **Documented asymptomatic hypoglycemia:** An event not accompanied by typical symptoms of hypoglycemia but with PG  $\leq 70$  mg/dL ( $\leq 3.9$  mmol/L).
- **Documented unspecified hypoglycemia:** An event during which PG  $\leq 70$  mg/dL ( $\leq 3.9$  mmol/L) but no information relative to symptoms of hypoglycemia was recorded.

**Probable symptomatic hypoglycemia:** An event during which symptoms typical of hypoglycemia are not accompanied by a PG determination but that was presumably caused by a PG concentration  $\leq 70$  mg/dL ( $\leq 3.9$  mmol/L).

**Relative hypoglycemia (also referred to as Pseudohypoglycemia):** An event during which the person with diabetes reports any of the typical symptoms of hypoglycemia with a measured PG concentration  $> 70$  mg/dL ( $> 3.9$  mmol/L) but approaching that level.

**Overall hypoglycemia:** This optional category combines all cases of hypoglycemia (documented hypoglycemia and probable symptomatic hypoglycemia, including severe hypoglycemia) excluding the events of relative hypoglycemia. Nocturnal and severe hypoglycemia are special cases of documented or probable hypoglycemia. If an event of hypoglycemia falls into multiple subcategories, that event should only be counted once in this category.

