#### **12.2.9.4. Hypoglycemic Events**

The incidence, rate per 30 days and rate per year of hypoglycemic episodes (total, severe, and nocturnal as defined in Section 9.10) will be summarized by treatment at baseline, titration, maintenance, and overall study periods and at endpoint. The rate per 30 days between two visits is defined as the total number of episodes between the visits divided by the actual number of days between the visits, and then multiplied by 30 days.

The proportion of patients (with at least 1 hypoglycemic event (total, severe, nocturnal, and others) or incidence during the study will be summarized (counts and percentages) and analyzed using Fisher's exact test or the Pearson's chi-square test for the FAS population.

The rate of hypoglycemic episodes per 30 days and per year (total, severe, nocturnal, and others) will be analyzed at baseline, titration, maintenance, and overall study periods and at endpoint

using the Wilcoxon test. In addition, the hypoglycemia rates will also be analyzed using a negative binomial model for the FAS population with terms for treatment, baseline HbA1c, and entry use of insulin secretagogues (SU, meglitinide, neither). The offset variables are log of patient's treatment duration/30 and log of patient's treatment duration/365.25 for the models analyzing hypoglycemia rate per 30 days and per year, respectively.

In addition, the total number of patients with at least 1 hypoglycemic episode divided by the total extent of exposure in patient-years will be calculated for the overall study period and summarized descriptively for each treatment group for total, severe, nocturnal, documented symptomatic, and asymptomatic hypoglycemia definitions only. Listings of hypoglycemic episodes will be presented by visit for each subject.

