5.2. Statistical and Analytical Plans

5.2.1. General Considerations

All data will be entered, verified, and archived by a contract research organization (CRO) external to Lilly and/or at Lilly. Data listings, summaries, and analyses will be performed by a CRO and/or by Lilly under the guidance and approval of statisticians at Lilly. Statistical analysis of this study will be the responsibility of Lilly.

Any change to the data-analysis methods described in the protocol will require an amendment ONLY if it changes a principal feature of the protocol. Any other change to the data analysis methods described in the protocol, and the justification for making the change, will be described in the statistical analysis plan and/or in the clinical study report (CSR). Additional exploratory analyses will be conducted as deemed appropriate.

The patient populations used in the study are described below:

1. All Patients Entered - all patients who signed ICF
2. All Randomized - all patients who were randomized to a treatment arm
3. Full Analysis Set (FAS) - based on the intent to treat (ITT) principle, all patients who were randomized and who have taken at least one dose of study medication will be included in this analysis set. Patients will be analyzed according to the treatments to which they were randomized.
4. Per-protocol (PP) - patients in the FAS/ITT population who also meet the criteria in Trial Issue Management Plan (TIMP), and treatment group will be defined on the basis of the treatment the patients actually receive:
 - a. have no violations of Inclusion/Exclusion Criteria specified in TIMP
 - b. have not discontinued from the study prior to 24 weeks
 - c. have not been off study medication for more than 14 consecutive days during the treatment period

- d. have not received chronic (lasting longer than 14 consecutive days) systemic glucocorticoid therapy (excluding topical, intra-articular, intraocular, and inhaled preparations)
- e. Missing HbA1c at baseline and/or at primary endpoint (week 24; only for subjects who should have V18)

Unless otherwise specified, listings will be prepared using all randomized patients. Efficacy and safety analyses will be conducted using the FAS population. Selected analyses will be conducted using the All Randomized population and the PP population.

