5.2.11.2. Hypoglycemic Events

A **hypoglycemic episode** is that at any time a patient feels as he/she is experiencing a sign or symptom that is associated with hypoglycemia or has a BG level of ≤ 70 mg/dL (≤ 3.9 mmol/L), even if it was not associated with signs, symptoms, or treatment.

Severe hypoglycemia: an event requiring assistance of another person to actively administer carbohydrates or glucagon or take other corrective actions. Plasma glucose concentrations may not be available during an event, but neurologic recovery following the return of plasma glucose to normal levels is considered sufficient evidence that the event was induced by low plasma glucose concentration.

Nocturnal hypoglycemia: any total hypoglycemic event that occurs after bedtime and prior to the first meal upon waking (eg, breakfast).

Documented symptomatic hypoglycemia: an event during which typical symptoms of hypoglycemia are accompanied by a measured plasma glucose concentration ≤ 70 mg/dL (≤ 3.9 mmol/L).

Asymptomatic hypoglycemia: an event not accompanied by typical symptoms of hypoglycemia but with a measured plasma glucose concentration ≤ 70 mg/dL (≤ 3.9 mmol/L).

Probable symptomatic hypoglycemia: an event during which symptoms typical of hypoglycemia are not accompanied by a plasma glucose determination but that was presumably caused by a plasma glucose concentration ≤ 70 mg/dL (≤ 3.9 mmol/L).

Besides the hypoglycemic categories listed above, total hypoglycemic event will be defined as follows:

Total hypoglycemic event: any event which is either documented symptomatic hypoglycemia, asymptomatic hypoglycemia, probable symptomatic hypoglycemia or severe hypoglycemia.

For each category of hypoglycemia event, the incidence, the number of hypoglycemic events per patient, the rate of hypoglycemic events per year (that is, the number of hypoglycemic episodes per patient per patient year [365.25 days]) will be calculated. These measures will be summarized at baseline, titration, maintenance, and overall study periods and at endpoint.

The proportion of patients with at least 1 hypoglycemic event (total, severe, nocturnal, and others) or incidence during the study will be summarized (counts and percentages) and analyzed using Fisher's exact test or the Pearson's chi-square test for the FAS population.

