Logistic regression will be used as a sensitivity analysis of the incidence of hypoglycemia. The model will have presence or absence of hypoglycemia as the dependent or response variable and treatment, baseline HbA_{1c}, and entry use of insulin scretagogue (SU, meglitinide, neither) as the independent terms in the model.

The rate of hypoglycemic episodes per year (total, severe, nocturnal, and others) will be analyzed at baseline, titration, maintenance, and overall study periods and at endpoint using the Wilcoxon test. In addition, the hypoglycemia rates will also be analyzed using a negative binomial model for the FAS population with terms for treatment, baseline HbA_{1c}, and entry use of insulin scretagogue (SU, meglitinide, neither).

In addition, the total number of patients with at least 1 hypoglycemic episode divided by the total extent of exposure in patient-years will be calculated for the overall study period and summarized descriptively for each treatment group for total, severe, nocturnal, documented symptomatic, asymptomatic hypoglycemia and probable symptomatic hypoglycemia. Individual patient listing of hypoglycemic events by visit will be presented for the FAS population.

All the above analysis will be repeated with the threshold of **Clinically significant hypoglycemia:** < 54 mg/dL (3.0 mmol/L) for hypoglycemia categories of total hypoglycemia,

nocturnal hypoglycemia, documented symptomatic hypoglycemia and asymptomatic hypoglycemia.

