The treatment-emergent antibody response (denoted TEAR throughout this SAP) is based on the change from baseline to post-baseline in the anti-insulin antibody level (percent binding). TEAR can be sub-classified as either treatment-induced (not detected anti-insulin antibody at baseline) or treatment-boosted (detected anti-insulin antibody at baseline):

- treatment-induced response: change from not detected anti-insulin at baseline to post-baseline detected anti-insulin;
- treatment-boosted response: change from detected anti-insulin at baseline to post-baseline detected anti-insulin antibody level (percent binding) at least 147% of the baseline value.

The number and proportion of patients who have a treatment-emergent antibody response (TEAR) will be summarized by treatment at each post-baseline visit, at the 24-week endpoint (LOCF), and overall for the 24-week treatment period, then analyzed using Fisher's exact test or Pearson's chi-square test.

For patients with TEAR, a visit-wise listing of total and cross-reactive insulin antibody percent binding and clinical outcomes (HbA_{1c}, total hypoglycemia rate, basal insulin dose (U/Day, U/kg/Day) will be presented. The listing will be sorted by treatment and endpoint total insulin percent binding.

Incidence tables showing the number and percent of patients with initial and continuing TEAR at each visit will be presented. Similar analyses will be performed for the detection of total insulin antibodies and for the detection of cross reactive insulin antibodies.

Box plots of clinical outcomes (HbA_{1c}, total hypoglycemia rate, basal dose) will be generated by treatment and TEAR status.

In addition, the following patient listings of insulin antibodies (percent binding) will be provided for patients with TEAR: a listing of level of total insulin antibody percent binding across visit sorted by treatment and maximum postbaseline percent binding; a listing of level of total insulin antibody percent binding across visit sorted by treatment and endpoint percent binding. Similar listings will be presented for cross reactive percent binding.

In addition, the potential impact of total insulin antibody level and TEAR status on clinical response will be evaluated in several ways:

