5.2.12. Subgroup Analyses

The consistency of the treatment effect for the change in HbA_{1c} level will be assessed within subgroups in the FAS population if there are sufficient numbers of patients in each subgroup (e.g. 20 patients per cell). The following subgroups will be analyzed:

- Entry HbA_{1c} levels (<8.5%, ≥8.5%)
- Entry BMI (<28, ≥28)
- Entry BMI (<24, ≥24)
- Entry age (<65, ≥65)
- Gender
- Entry use of insulin secretagogues (SU, meglitinide, neither)
- Renal function, as estimated by estimated glomerular filtration rate (EGFR) using the MDRD formula (see [Appendix 2](#)). The following EGFR categories will be used:
 - Normal or increased GFR: EGFR (≥90 mL/min/1.73 m²)
 - Mild reduction in GFR: EGFR (60-89 mL/min/1.73 m²)
 - Moderate reduction in GFR: EGFR (30-59 mL/min/1.73 m²)
 - Severe reduction in GFR: EGFR (15-29 mL/min/1.73 m²)
 - Kidney failure: EGFR (<15 mL/min/1.73 m²).

The categories of severe reduction in GFR and kidney failure will be combined if there are fewer than 20 patients in either of these categories.

The change in HbA_{1c} from baseline to 24-week endpoint will be analyzed using MMRM with treatment (LY2963016, Lantus®), entry use of insulin secretagogue (SU, meglitinide, neither), visit, subgroup, subgroup-by-treatment interaction, subgroup-by-visit interaction, treatment-by-visit interaction, and treatment-by-visit-by-subgroup interaction as fixed-effects; the baseline value of HbA_{1c} as a covariate, and a random effect for patient for the FAS. If the subgroup is one of the stratification variables, then the subgroup will only be included once in the model. A significant treatment-by-subgroup interaction (p<.05) may be indicative of a differential treatment effect across levels of the subgroup, necessitating further exploration of the nature of the interaction.

For each subgroup listed above, the change in weight from baseline to 24-week will be analyzed using the same methodology as the subgroup analysis of HbA_{1c}, except baseline weight will be added as another covariate.

Additional subgroup analyses will be carried out on selected safety outcomes:

- a) total or nocturnal hypoglycemia at 24-week endpoint and for the overall 24-week period (rates and incidence)
- b) treatment-emergent antibody response (TEAR) at 24-week endpoint and for the overall 24-week period
- c) detectable insulin antibodies at 24-week endpoint and for the overall 24-week period
- d) categories of adverse events:

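### The SAP's definition of total hypoglycemia omits the protocol's documented unspecified category, so, read literally, non-severe low readings with unrecorded symptoms drop out of total and the analyses built on it

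*SAP*

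**What the plan says.** Protocol 9.10 has three kinds of documented event, all with plasma glucose of 70 mg/dL or less: symptomatic, asymptomatic and unspecified. Unspecified means the glucose value is there "but no information relative to symptoms of hypoglycemia was recorded". The section then gives one pooled category, called overall and labelled optional, which "combines all cases of hypoglycemia (documented hypoglycemia and probable symptomatic hypoglycemia, including severe hypoglycemia") and leaves out relative hypoglycemia. Protocol 12.2.9.4 plans that "hypoglycemic episodes (total, severe, and nocturnal as defined in Section 9.10) will be summarized by treatment".

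SAP 5.2.11.2 opens by counting any glucose of 70 mg/dL or less as a hypoglycemic episode, with or without symptoms. Its category list has no unspecified category. A total event is "any event which is either documented symptomatic hypoglycemia, asymptomatic hypoglycemia, probable symptomatic hypoglycemia or severe hypoglycemia". Nocturnal events are defined as a subset of total events.

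Total is used widely:
- SAP 5.2.11.2 uses it for incidence and rates, and adds that "All the above analysis will be repeated with the threshold of" <54 mg/dL for total and nocturnal, among others.
- SAP 5.2.12 plans subgroup analyses of "total or nocturnal hypoglycemia at 24-week endpoint and for the overall 24-week period (rates and incidence").
- SAP 5.2.11.4 includes it among the clinical outcomes in the box plots (HbA1c, "total hypoglycemia rate, basal dose) will be generated by treatment and TEAR status") and in the antibody regressions.

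For departures from the protocol's analysis methods, SAP 5.2.1 says that the change "and the justification for making the change, will be described in the statistical analysis plan and/or in the clinical study report (CSR").

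The two documents also bound nocturnal events differently. Protocol 9.10 ends the window at waking. The SAP extends it to the first meal after waking.

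**The concern.** The SAP's list for total is closed. A non-severe reading of 70 mg/dL or less with no symptom information is an episode under the SAP's opening definition and a documented event under the protocol, yet it fits none of the four components of total. It is not documented symptomatic. It is not probable symptomatic, because a glucose value exists. Asymptomatic requires that typical symptoms were absent, which is not the same as not recorded, and the protocol keeps the two apart. The SAP has no rule for a blank symptom field, so the programmer has to choose.

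Such events are foreseeable. The protocol created a category for them, patients test fasting glucose daily and complete 4-point and 7-point profiles, and symptom information depends on the diary.

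Hypoglycemia is a named secondary safety objective, and the omission passes into every analysis that uses total. The SAP gives no reason for it. Its revision history names the hypoglycemia categories deleted in version 2, and unspecified is not among them. That history covers only the step from version 1 to version 2, so the omission may be older.

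**Working it through.** The plan states no figure on this point, so there is none to reproduce.

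**1. Which events differ.** Cross severity (no, yes), symptoms (present, absent, not recorded) and glucose (≤70 mg/dL, >70 mg/dL, missing): 2 × 3 × 3 = 18 cells. The nine severe cells count under both definitions. The nine non-severe cells are:

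| Non-severe event | Protocol overall | SAP total |
|---|---|---|
| Symptoms present, ≤70 | in | in |
| Symptoms absent, ≤70 | in | in |
| **Symptoms not recorded, ≤70** | **in** | **out** |
| Symptoms present, glucose missing | in | in |
| Symptoms present, >70 (relative, if near 70) | out | out |
| Symptoms absent or not recorded, >70 or missing (4 cells) | out | out |

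The definitions agree in 17 of 18 cells. Adding documented unspecified to the SAP list gives 18 of 18.

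**2. Effect on rates.** Let s be the share of protocol-defined events in an arm that are non-severe and unspecified. The literal SAP rate is the protocol rate × (1 − s), so it can only be equal or lower. The rate ratio (LY2963016 to Lantus) is multiplied by (1 − s for LY2963016)/(1 − s for Lantus). The documents give no value for s. I assume 0% to 10% per arm.

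| s, LY2963016 | s, Lantus | Multiplier |
|---|---|---|
| 0%, 5% or 10% | the same | 1.00 |
| 5% | 10% | 0.95/0.90 = 1.056 |
| 10% | 5% | 0.90/0.95 = 0.947 |
| 0% | 10% | 1.00/0.90 = 1.111 |
| 10% | 0% | 0.90/1.00 = 0.90 |

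**3. Effect on incidence.** Incidence changes only for patients whose sole events are unspecified. As an illustration, let events be Poisson with mean m per patient (assumption). Incidence is then 1 − exp(−m) under the protocol definition and 1 − exp(−m(1 − s)) under the literal SAP list.

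| m | Protocol | SAP, s = 5% | SAP, s = 10% |
|---|---|---|---|
| 0.5 | 39.3% | 37.8% | 36.2% |
| 1 | 63.2% | 61.3% | 59.3% |
| 2 | 86.5% | 85.0% | 83.5% |
| 4 | 98.2% | 97.8% | 97.3% |

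The fall is 0.4 to 1.9 percentage points at s = 5% and 0.9 to 3.9 points at s = 10%. The SAP's own rate model is negative binomial. With dispersion 1 (assumption), incidence is 1 − 1/(1 + m). At s = 10% and m = 1 it goes from 1 − 1/2 = 50.0% to 1 − 1/1.9 = 47.4%, a fall of 2.6 points. At m = 4 it goes from 1 − 1/5 = 80.0% to 1 − 1/4.6 = 78.3%, a fall of 1.7 points. The order of magnitude is the same.

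**4. Nocturnal window.** The fasting check required daily by Protocol 7.2.3 can fall after waking and before breakfast. A low reading then is nocturnal under the SAP but not under Protocol 9.10. The number of such readings cannot be derived from the documents.

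**The case against.** Protocol 9.10 never defines total. It defines overall and calls it optional, so the SAP can be read as filling a gap rather than changing a definition. This is fair as to wording. But 12.2.9.4 refers to 9.10 for total, and overall is the only pooled category there.

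Blanks may in practice be coded as asymptomatic, which would remove the loss. Symptoms are meant to be recorded for each episode, sites review diaries, and hypoglycemia is asked about at telephone visits, so blanks may also be few. These points stand as limits on the size. They do not supply the missing rule.

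The SAP's reference list includes an unpublished sponsor white paper on classifying hypoglycemia events, which may contain such a rule. SAP 5.2.11.2 does not cite it, so it cannot be relied on here. The justification may also appear in the CSR, as SAP 5.2.1 allows, so its absence from the SAP is not in itself a breach.

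The 0% to 10% range has no basis in the documents, and the extreme multipliers need 10% in one arm and none in the other, with no mechanism offered. That is correct. In an open-label trial equal recording cannot be taken for granted, but nothing shows that it differs.

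The nocturnal conflict is a separate and lesser point. It applies the same rule to both arms and changes only a sub-label.

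**Conclusion.** The concern holds on the literal text. One type of event, the non-severe reading of 70 mg/dL or less with unrecorded symptoms, counts in the protocol's pooled category and is absent from the SAP's total and everything derived from it. Severe events are counted either way. Absolute total rates can only be equal or lower than under the protocol definition. Whether the treatment comparison moves depends on whether the share of such events differs between arms. The effect may be anywhere from nil to the figures above, which rest on assumed shares and means. Confidence is high in the gap in the text and low in its practical size.

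The conflict between the nocturnal windows is also real, though it cannot be sized. None of this touches the primary HbA1c test. It should be fixed because a stated rule undercounts confirmed low readings on a named safety objective and the remedy is simple.

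**What to change.** Before database lock, add documented unspecified hypoglycemia (glucose of 70 mg/dL or less, symptoms not recorded) to the category list and to the definition of total in SAP 5.2.11.2, and carry it into the repeat at <54 mg/dL. Nocturnal, the subgroup analyses and the antibody analyses then follow through total. If the intention was to code blanks as asymptomatic, the SAP should say so and justify the difference from Protocol 9.10; that too would keep the events in total.

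Separately, reconcile the two nocturnal definitions. State and justify which window is the main analysis, and report the other as a sensitivity summary if the collected times allow.

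The category change needs a few lines of SAP text and programming and no new data. Reported total rates may rise slightly. The nocturnal summary is conditional: per episode, Protocol 9.10 asks for glucose, symptoms, treatment and outcome, and the documents do not show that waking time is collected. The same is true of bedtime and first-meal time, so the sponsor should confirm what was recorded before choosing.

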5.2.11.3. Laboratory Measures – Chemistry/Hematology Panel

Continuous measures and their change from baseline to 24-week endpoint in the chemistry and hematology panels for the FAS population will be summarized using descriptive statistics at baseline and at 24-week endpoint for the FAS population.

The continuous measures and change from baseline values to 24 weeks will be analyzed using the ANCOVA model with treatment, entry use of insulin secretagogues (SU, meglitinide, neither) as fixed effects and the baseline value of HbA1c and the baseline of the response variable as covariates.

For each chemistry and hematology analyte, the number and percent of patients with treatment emergent high (not in high range at baseline, greater than the upper limit at Week 24/Early Discontinuation) and treatment emergent low (not in low range at baseline, less than the lower limit at Week 24/Early Discontinuation) will be presented and analyzed using Fisher's exact test or Pearson's chi-square test. Unscheduled safety lab results will be included in the analysis.

